2.3 Study plan

Table 2 Trial flow chart

Trial Period	Screening	Treatment phase				Follow-up	Unscheduled visit ^g	
Day	(Day - 28 to -3)	Day 1	Day 28 (±2 days)	Day 56 (±2 days)	Day 84 (±5 days)	Day 112 (±2 days)		
Procedure	Visit Number	1	2	3	4	5	6	Unscheduled
Informed consent		X						
In-/exclusion criteria		X	X					
Demographics/medical history		X						
Physical examination		X	X			X	X	
Height, body weight, BMI		X						
Smoking history/ alcohol consumption		X						
Vital signs		X	X	X	X	X	X	
Pregnancy test in female patients ^a		X	X ^b			X		
Safety laboratory, incl. urine dipstick		X	X	X	X	X	X	X
HIV, Hepatitis		X						
Randomization			X					
Localization of photographic documentation test field ^c			X					
Photographic documentation ^c			X	X	X	X	X	
PK sample ^d			X			X		
PASI		X	X	X	X	X	X	
PGA		X	X	X	X	X	X	
BSA		X	X	X	X	X	X	
Dispensing of IMP			X	X	X			
IMP administration ^e			X	X	X	X		
Diary dispensing			X	X	X			
Drug return / accountability				X	X	X		
Diary return and check				X	X	X		
Prior and concomitant therapy		X	X	X	X	X	X	X
Adverse events ^f		X	X	X	X	X	X	X

- a) A serum pregnancy test will be done for all women at screening and urine test for all other visits.
- b) A urine pregnancy test on Day 1 will be performed prior to the first administration of IMP for all women.
- c) Only performed in a subgroup of approx. 2 sites (approx. 30 patients); on Day 1 Photographic documentation will be performed prior to the first administration of IMP
- d) Only performed in a subgroup of approx. 4 sites (approx. 30 patients); on Day 1 and Day 84 first PK sample will be performed prior to the first administration of IMP. PK samples will be collected before IMP administration, and 15, 30, 60 and 120 minutes after administration of IMP.
- e) IMP administration will start on Day 1 after randomization and will continue as self-administration by trial patients at home until Day 84. Patients included in the PK analysis will administrate the first treatment (Day 1) at the site. All patients will administrate the last treatment (Day 84) at the sites.
- f) AE reporting starts after the signature of informed consent form and finishes at the End of Study Follow-Up Visit.
- g) Perform assessments which are relevant to the reason for the unscheduled visit (e.g. Photographic documentation, Lab analysis, PASI, PGA, BSA, etc.).

3 Statistical and analytical procedures

3.1 Definitions

The following definitions apply:

- Baseline: The latest non-missing observation prior to first treatment with IMP.

Baseline data definition	obtained on/at
Age, race, height, body weight, BMI	Screening
Relevant medical history (last 5 years) including psoriasis history, relevant surgical history (last 5 years) and relevant previous medication (last 6 weeks) including psoriatic treatment taken (last 6 weeks)	Screening
Smoking and alcohol consumption	Screening
Concomitant medication	Day 1
Adverse events	Day 1
Physical examination	Day 1, Screening*
Vital signs (blood pressure, pulse rate)	Day 1, Screening*
Safety laboratory parameters	Day 1, Screening*
PASI, PGA, BSA	Day 1, Screening*

*only in case of missing Day 1 assessment

- Change from baseline = post baseline value – baseline value
- Percent change from baseline = $100 * \text{change from baseline} / \text{baseline value}$
- Last observation carried forward (LOCF): The last observed value (either scheduled or unscheduled) carried forward and used for all directly subsequent and missing scheduled points.
- Current medical conditions – medical conditions ongoing at first dosing.
- Prior therapy: Any medication or therapy taken prior to start of first IMP dosing.
- Concomitant therapy: A medication or therapy ongoing at start of first IMP dosing, or starting after the first IMP dosing.
- Treatment emergent adverse event (TEAE): Adverse event with an onset (or worsening) on or after the time of the first IMP dosing.
- Time to achievement of PASI 50 (75): Day of first visit were PASI 50 (75) is observed.
- Analysis centers: Pooled small centers for analyses, as described in section 3.5.4.

3.2 Analysis variables

3.2.1 Efficacy variable(s)

3.2.1.1 Psoriasis Area Severity Index (PASI)

The PASI quantifies the severity and extent of the disease and weighs these with the body surface area involvement. It involves the assessment of erythema (E), infiltration (I),

desquamation (D), and body surface area involvement (A) over 4 body regions: head (h), trunk (t), upper (u) and lower extremities (l).

Degree of severity (for E, I, D) per body region	Value given
No symptoms	0
Slight	1
Moderate	2
Marked	3
Very marked	4

Surface involved (A), per body region	Value given
<10%	1
10-29%	2
30-49%	3
50-69%	4
70-89%	5
90-100%	6

Because the head (h), upper extremities (u), trunk (t), and lower extremities (l) correspond to approximately 10%, 20%, 30%, and 40% of body surface area, respectively, the PASI score is calculated by the formula:

$$\text{PASI} = 0.1*(\text{Eh} + \text{Ih} + \text{Dh})*\text{Ah} + 0.2*(\text{Eu} + \text{Iu} + \text{Du})*\text{Au} + 0.3*(\text{Et} + \text{It} + \text{Dt})*\text{At} + 0.4*(\text{Ei} + \text{Ii} + \text{Di})*\text{Al}$$

The PASI score ranges from 0 to 72, with a higher score indicating increased disease severity and will be assessed at the time points specified in Table 2.

3.2.1.2 Physician's Global Assessment (PGA)

The PGA provides an overall evaluation of the severity of the disease. The PGA is a 7-point physician's assessment of psoriasis that is a therapeutic standard in clinical studies for this disease.

Disease severity	Value given
Clear	0
Almost clear	1
Mild	2
Mild to moderate	3
Moderate	4
Moderate to severe	5
Severe	6

The PGA will be completed by the Investigator (or designee) at the time points specified in Table 2.

3.2.1.3 Assessment of body surface area (BSA)

The total surface area of the body affected with psoriasis plaques will be determined by the Investigator at the time points specified in Table 2. The investigator will calculate the approximate BSA by assuming that 1% BSA is approximately equal to the surface area of one outstretched hand (with fingers) of the patient [2]. Calculation should include psoriasis on the palms of the hands and soles of the feet as well as on the face and scalp.

The assessment of BSA by the Investigator serves to describe the change in % BSA affected by psoriasis after 12 weeks of treatment.

3.2.1.4 Primary efficacy variable(s)

The primary efficacy variables are:

1. 75% improvement (response) in their PASI score (PASI 75) and
2. Improvement (1 or more points on a 7 point scale) in their PGA score

The secondary efficacy variables are:

3. 50% improvement (response) in their PASI score (PASI 50)
4. Mean PASI score and change to baseline
5. Time to achieve PASI 50 and PASI 75
6. Mean score and change from baseline in the PGA
7. Mean score and change from baseline in the BSA
8. PK data

3.2.2 Safety variables

3.2.2.1 Adverse events

All noted complaints will be recorded with duration, intensity/severity, seriousness, probability of relatedness to the study preparation and outcome (see study protocol, section 7.3., Reporting/documentation of adverse events).

As it is the case for expedited reporting (see study protocol section 7.3.1) adverse events with a causal relationship to IMP described as “probable” or “possible” will like a “certain” causality be considered as “related” whereas an “unlikely” causality will be considered as “not related”, if applicable.

3.2.2.2 Laboratory variables

The following laboratory parameters will be collected at every visit (except serology):

Table 3 Laboratory Parameter per visit

Parameter	Screening	Day 1	Day 28 / 56	Day 84 (EoT)	Day 112 (FU)
Serology					
Hepatitis A IgG-antibody-test	X	--	--	--	--
Hepatitis A IgM-antibody-test	X	--	--	--	--
Hepatitis B core antibody-test	X	--	--	--	--
Hepatitis B surface antibody-test	X	--	--	--	--
Hepatitis B surface antigen-test	X	--	--	--	--
Hepatitis C virus antibody-test	X	--	--	--	--
HIV-1 antibody-test	X	--	--	--	--
HIV-2 antibody-test	X	--	--	--	--
Hematology					
RBC	X	X	X	X	X
WBC* including differential	X	X	X	X	X
Hemoglobin	X	X	X	X	X
Hematocrit	X	X	X	X	X

Parameter	Screening	Day 1	Day 28 / 56	Day 84 (EoT)	Day 112 (FU)
MCH	X	X	X	X	X
MCV	X	X	X	X	X
MCHC	X	X	X	X	X
Platelets	X	X	X	X	X
Clinical Chemistry					
AST (GOT)	X	X	X	X	X
ALT (GPT)	X	X	X	X	X
γGT	X	X	X	X	X
AP	X	X	X	X	X
Creatinine	X	X	X	X	X
Total bilirubin	X	X	X	X	X
CRP	X	X	X	X	X
hCG serum	X	--	--	--	--
Urine					
Urine dip stick test**	X	X	X	X	X

* including lymphocyte, neutrophils count, and eosinophils

** leukocytes, nitrite, pH, protein, glucose, ketones, urobilinogen, bilirubin, blood/hemoglobin

3.2.2.3 Pharmacokinetic variables

To evaluate systemic concentrations of MP1032 PK samples will be analyzed in a subgroup at selected trial sites, approximately 30 patients in total.

Blood will be collected before morning dose and 15, 30, 60 and 120 minutes after morning dose at visit 2 (Day 1, baseline) and at visit 5 (Day 84, end of treatment [EoT]). The date and time of the last application of IMP prior to the PK sample taken and the date and time of the PK sample will be documented in the electronic case report form (eCRF).

Samples will be analyzed at Prolytic GmbH, Frankfurt and the results of blood MP1032 concentration will be transferred to bioskin for statistical analysis.

3.2.2.4 Other safety variables

Physical examination focusing on the skin is done at screening, Day 1, Day 84, and at follow up visit (Day 112).

Vital signs (blood pressure and pulse rate) will be assessed at all visit days planned.

3.3 Analysis populations

3.3.1 Efficacy populations

Intent-To-Treat (ITT)

The full-analysis-set (FAS) will include all randomized patient who received at least one dose of IMP, and had at least one post-baseline assessment. The intention-to-treat (ITT) analysis will be based on the FAS. The FAS is considered primary analysis set for the efficacy analysis.

Per-Protocol (PP)

The valid-cases-set (VCS) will include all patients from the FAS, who completed the assessments of the co-primary endpoints without any protocol violation interfering with the precise evaluation of treatment efficacy and with sufficient exposure to IMP, i.e.

- who completed the visit 5 (Day 84) assessments of PASI and PGA;
- who did not take any prohibited concomitant medications up to the visit 5 (Day 84).

During the blind data review meeting (BDRM) concomitant medications will be reviewed considering timing, duration of concomitant treatment, and influence on the efficacy assessments to determine prohibited medication usage that warrants exclusion from the VCS;

- who were compliant with the dosing regimen. A subject will be considered compliant, if the subject administered $\geq 80\%$ of the planned capsules.

Subjects who prematurely discontinue the treatment due to an adverse event at least possibly related to IMP will not be excluded from the VCS.

Prior to breaking the blind, other additional criteria may be added to the list to accommodate for unforeseen events that occurred during the conduct of the trial that result in noteworthy study protocol violations.

The per-protocol (PP) analysis will be based on the VCS. Primary efficacy endpoints will be evaluated on VCS to assess the sensitivity.

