5.3.5.2 Criteria for discontinuing in the case of individual patients

Patients may withdraw from the entire trial including follow-up at any time without penalty and for any reason without prejudice to his or her future medical care.

The following criteria must lead to discontinuation from the clinical trial in individual patients:

- Patient withdraws informed consent

- Pregnancy (see section 7.4)
- Severe protocol violations that result in a significant risk to the patient's safety
- Emergence of the following AEs including:
 - a) Patient reports symptoms which are considered unacceptable by the patient or the Investigator or if any serious AE occurs that is judged as at least possibly related to the IMP by the Investigator
 - b) Abnormal laboratory value(s) confirmed by repeat measurements:
 - Elevated liver transaminases (AST/ALT) $\geq 3 \times$ ULN AND elevated bilirubin total bilirubin $\geq 2 \times$ ULN
 - Elevated serum creatinine $\geq 2 \times$ ULN

The following criteria may lead to discontinuation from the clinical trial in individual patients:

- Use of prohibited concomitant medication as defined in section 5.4.5.

In all cases, the reason(s) for withdrawal, and the primary reason, must be recorded on the electronic data capture (EDC) system / electronic case report form (eCRF). If a patient is prematurely withdrawn from the IMP for any reason, the Investigator must make every effort to perform the evaluations described for the End of Treatment and Follow-up Visits. The Investigator should contact the Medical Monitor, whenever possible, to approve withdrawal of patients in advance.

If a patient withdraws consent and still agrees to undergo a final examination, it will be documented on the eCRF and the patient record.

A patient may also be withdrawn from the IMP by the Sponsor, Regulatory Authorities, or Independent Ethics Committees (IECs) / Institutional Review Boards (IRBs).

Patients who are withdrawn from the trial will be not replaced.

Protocol violation, failure to comply with the trial stipulations/poor compliance may lead to discontinuation from the clinical trial in individual patients.

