5.5 Efficacy and safety variable(s)

5.5.1 Procedures

Screening period

Day -28 to -3 (visit 1)

Within the 28 days prior to the first IMP administration the volunteer will come to the trial centers for the initial screening (including documentation of demographic data). Screening assessments will be performed after the volunteer has agreed to participate and has signed and dated the informed consent form.

At screening a serum pregnancy test will be carried out in all female patients.

The following examinations will be performed:

- Obtain written informed consent
- Documentation of relevant medical and relevant surgical history (last 5 years)
- Documentation of demographic data
- Documentation of Smoking history/ alcohol consumption
- Documentation of relevant previous medication (last 6 weeks)
- Serum pregnancy test and urinalysis (see section 5.5.2)
- Start check in-/exclusion criteria (see section 5.3.2 and 5.3.3)
- Physical examination (see section 5.5.5)
- Height, body weight and BMI
- Record vital signs (see section 5.5.3)
- PASI (see section 5.5.1.1)
- PGA (see section 5.5.1.2)
- BSA (see section 5.5.1.3)

- Collection of samples for determination of laboratory parameters (serology, hematological status, clinical chemistry, see section 5.5.2).

Note: Adverse events before start of treatment (i.e. occurring after signature on consent form). Patients who have abnormal test results during the screening period may be re-screened if the Medical Monitor agrees.

Experimental phase

Trial Day 1 (baseline, week 1, visit 2)

- Re-check of in-/exclusion criteria (see section 5.3.2)
- Randomization
- Physical examination (see section 5.5.5)
- Record vital signs (see section 5.5.3)
- Urine pregnancy test and urinalysis (see section 5.5.2)
- Record concomitant medications
- Record adverse events occurring from the time of informed consent signature
- *Localization of photographic documentation test field only for a subgroup (see section 5.5.1.4)*
- *Photographic documentation only for a subgroup (see section 5.5.1.4)*
- Collection of samples for determination of laboratory parameters (hematological status, clinical chemistry, see section 5.5.2)
- PASI (see section 5.5.1.1)
- PGA (see section 5.5.1.2)
- BSA (see section 5.5.1.3)
- Dispensing diary
- *Start of PK samples only for a subgroup (see section 5.5.1.5)*
- Dispensing IMP
- *Administration of IMP at site (PK subgroup only)*

Trial Day 28 (week 4, visit 3) and Day 56 (week 8, visit 4)

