- Check concomitant therapy and adverse events
- Record vital signs
- Drug return / accountability and re-dispensation of unused kits/blister
- Diary collected and checked
- *Photographic documentation only for a subgroup (see section 5.5.1.4)*
- Urinalysis (see section 5.5.2)
- Collection of samples for determination of laboratory parameters (hematological status, clinical chemistry, urinalysis, see section 5.5.2)
- PASI (see section 5.5.1.1)

- PGA (see section 5.5.1.2)
- BSA (see section 5.5.1.3)
- Dispensing of IMP and diary

Trial Day 84 (week 12, visit 5) (EoT)

- Check concomitant therapy and adverse events
- Physical examination (see section 5.5.5)
- Record vital signs (see section 5.5.3)
- Urine pregnancy test and urinalysis (see section 5.5.2)
- *Photographic documentation only for a subgroup (see section 5.5.1.4)*
- Collection of samples for determination of laboratory parameters (hematological status, clinical chemistry, see section 5.5.2)
- *PK samples only for a subgroup (see section 5.5.1.5)*
- Last IMP administration at site for all patients
- Drug return / accountability
- Diary collected and checked
- PASI (see section 5.5.1.1)
- PGA (see section 5.5.1.2)
- BSA (see section 5.5.1.3)

Trial Day 112 (week 16, visit 6, Follow-up) (End of Study, EoS)

- *Photographic documentation only for a subgroup (see section 5.5.1.4)*
- Check concomitant therapy and adverse events
- Physical examination (see section 5.5.5)
- Record vital signs (see section 5.5.3)
- Urinalysis(see section 5.5.2)
- Collection of samples for determination of laboratory parameters (hematological status, clinical chemistry, see section 5.5.2)
- PASI (see section 5.5.1.1)
- PGA (see section 5.5.1.2)
- BSA (see section 5.5.1.3)

The patients must be present at site for approximately 60 minutes on Screening and Day 1, 45 minutes on Day 28 and 56, 60 minutes on Day 84 and 45 minutes on Day 112.

The above mentioned time will be extended for 15 minutes for patients with photographic documentation on each visit.

The above mentioned time will be extended on Day 1 and Day 84 for 120 minutes for patients with PK sampling.

Early Termination Visit

Patients who discontinue early from the trial should, if possible, have an Early Termination Visit. This visit should take place as soon as possible after the patient stops taking IMP. The observations and procedures scheduled for Visit 5 (End of Treatment) should be performed at the Early Termination Visit.

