6.2 Analysis sets and type of analysis

The safety-evaluation-set (SES) will include all patients who received any trial medication at least once; all safety analyses will be based on the SES.

The full-analysis-set (FAS) will include all randomized patient who received at least one dose of IMP, and had at least one post-baseline assessment. The intention-to-treat (ITT) analysis will be based on the FAS.

The valid-cases-set (VCS) will include all patient from the FAS, without any protocol violation interfering with the trial aims and with sufficient exposure to IMP. The per-protocol (PP) analysis will be based on the VCS.

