3.5.1 Missing data

A description of missing data will be provided in the clinical study report.

For the evaluation of success rates of the primary efficacy variables PASI and PGA missing PGA assessments and/or any parts of the PASI assessments will be evaluated as failure to achieve improvement.

For descriptive analyses of PASI, PGA and BSA the last observation carried forward (LOCF) principle will be applied to impute the missing assessments, up to the Day 84 visit. Follow-up assessments will not be imputed.

Sensitivity of the primary efficacy analyses will be evaluated applying PP analyses.

Regarding incomplete recordings for adverse events the following rules apply:

- For start and stop dates no imputation will be applied. If any, start or stop date, is not complete, but required for the classification, i.e. the occurrence of the AE is not explicitly reported as occurring prior first dose (see eCRF), the AE will be considered treatment emergent.
- Missing assessments of severity, intensity and causal relationship to the IMP will be reported as a separate category.

For the determination of the number of years from start of psoriasis to the screening visit missing starting days will be imputed by the first day of month and missing months will be imputed by the first month (January) of the year.

For concomitant therapies (see section 3.2.2.4) incomplete dates will not be imputed. If an incomplete start or stop date does not allow for the classification as prior and/or concomitant therapy - despite of information in eCRF if taken/used prior to first dosing and/or if ongoing at first dosing - the treatment will be reported as prior and as concomitant therapy.

Pharmacokinetic data below LLQ will be replaced as described in 3.4.7.3 for descriptive statistics and for the derivation of $AUC_{(0,t)}$. Missing pre-dose levels will be imputed by zero. Missing intermediate samples, i.e. missing values in between non-missing levels (quantifiable or substituted by LLQ/2) will be imputed by linear interpolation between the last preceding and the next following available value. The last value will be imputed by LLQ/2, if missing.

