Withdrawal by subject	XX (XXX.X%)	XX (XXX.X%)	XX (XXX.X%)	XX (XXX.X%)
Other	XX (XXX.X%)	XX (XXX.X%)	XX (XXX.X%)	XX (XXX.X%)

EoT: End of treatment.

¹ Week 12/EoT visit of PASI within the time range 80 ≤ study day ≤ 91 and exposure ≥ 80% planned exposure

² Week 12/EoT visit of PASI at a study day ≤ 79 or exposure < 80% planned exposure

Source data: <DATASET> <DATE>

Program: <SAS PROGRAM> <DATE>

Table 14.1.4: Excluded subjects from the analysis populations (Randomized subjects)
(Part 1 of 1)

	MP1032 300 mg bid	MP1032 150 mg bid	Placebo bid	Total
Number of randomized subjects	N = XX	N = XX	N = XX	N = XX
Subjects excluded from the SES	XX (XXX.X%)	XX (XXX.X%)	XX (XXX.X%)	XX (XXX.X%)
Primary exclusionary reason / protocol deviation ¹				
Subject did not receive any IMP	XX (XXX.X%)	XX (XXX.X%)	XX (XXX.X%)	XX (XXX.X%)
Subjects excluded from the FAS	XX (XXX.X%)	XX (XXX.X%)	XX (XXX.X%)	XX (XXX.X%)
Primary exclusionary reason / protocol deviation ¹				
Subject did not receive any IMP	XX (XXX.X%)	XX (XXX.X%)	XX (XXX.X%)	XX (XXX.X%)
Subject has no post-baseline assessment	XX (XXX.X%)	XX (XXX.X%)	XX (XXX.X%)	XX (XXX.X%)
Subjects excluded from the VCS	XX (XXX.X%)	XX (XXX.X%)	XX (XXX.X%)	XX (XXX.X%)
Primary exclusionary reason / protocol deviation ¹				
Subject did not receive any IMP	XX (XXX.X%)	XX (XXX.X%)	XX (XXX.X%)	XX (XXX.X%)
Subject has no post-baseline assessment	XX (XXX.X%)	XX (XXX.X%)	XX (XXX.X%)	XX (XXX.X%)
Subject took interfering concomitant medication	XX (XXX.X%)	XX (XXX.X%)	XX (XXX.X%)	XX (XXX.X%)
Subject did not complete Week 12 visit (EoT)	XX (XXX.X%)	XX (XXX.X%)	XX (XXX.X%)	XX (XXX.X%)
Subject not compliant with dosing regimen ²	XX (XXX.X%)	XX (XXX.X%)	XX (XXX.X%)	XX (XXX.X%)
Other major protocol deviations	XX (XXX.X%)	XX (XXX.X%)	XX (XXX.X%)	XX (XXX.X%)
Subjects excluded from the PKS	XX (XXX.X%)	XX (XXX.X%)	XX (XXX.X%)	XX (XXX.X%)
Primary exclusionary reason / protocol deviation ¹				
Subject did not receive any IMP	XX (XXX.X%)	XX (XXX.X%)	XX (XXX.X%)	XX (XXX.X%)
Subject has no completed determination of MP1032 levels	XX (XXX.X%)	XX (XXX.X%)	XX (XXX.X%)	XX (XXX.X%)
Subject took interfering concomitant medication	XX (XXX.X%)	XX (XXX.X%)	XX (XXX.X%)	XX (XXX.X%)
Other major protocol deviations	XX (XXX.X%)	XX (XXX.X%)	XX (XXX.X%)	XX (XXX.X%)

¹ In case of multiple deviations, only the primary exclusionary reason / protocol deviation is counted;

² Subjects who had less than 80% of the expected oral doses.

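### The full analysis set requires a post-baseline assessment, so a dosed patient who stops before Day 28 and never returns leaves the co-primary denominator instead of counting as a failure

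*SAP*

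**What the plan says.** The SAP defines the primary set in section 3.3.1: "The full-analysis-set (FAS) will include all randomized patient who received at least one dose of IMP, and had at least one post-baseline assessment". It adds that "The FAS is considered primary analysis set for the efficacy analysis". Protocol 6.2 has the same condition: "had at least one post-baseline assessment. The intention-to-treat (ITT) analysis will be based on the FAS". Neither document says whether the required assessment must be an efficacy assessment.

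For the two co-primary responder endpoints, SAP 3.5.1 (and Protocol 6.6) says that "missing PGA assessments and/or any parts of the PASI assessments will be evaluated as failure to achieve improvement".

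The first scheduled visit after baseline is Day 28 (flow charts in both documents). On patients who stop earlier, Protocol 5.5.1 says: "Patients who discontinue early from the trial should, if possible, have an Early Termination Visit". Protocol 5.3.5.2 is firmer: it obliges the investigator to try hard to obtain the End of Treatment and Follow-up evaluations. It also says: "Patients who are withdrawn from the trial will be not replaced".

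Table 14.1.4 in the SAP appendix lists "Subject has no post-baseline assessment" as a reason for exclusion from the full analysis set, separate from not having received IMP. The exclusion is therefore planned. The only stated sensitivity analysis of the co-primary endpoints is per-protocol (SAP 3.3.1 and 3.5.1), and the valid cases set is selected from the full analysis set.

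**The concern.** A rule that scores missing data as failure can be applied to any patient, including one never seen after baseline. Requiring a post-baseline assessment first removes patients whom the rule would otherwise count as failures.

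Membership of the primary set then depends on something that happens after randomisation, namely whether the patient is seen again, and treatment can influence that. Each such exclusion raises the response rate of that patient's arm. If the exclusions differ between arms, the analysis labelled intention-to-treat gives a distorted difference. No planned analysis would show this, because responder tables are planned only for the full analysis set and the valid cases set.

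**Working it through.** **Inputs from the plan.** About 50 patients randomised per arm (Protocol 5.1, SAP 2.1). Example rates 0.674 v 0.40, two-sided level 0.10, 80% power, 40 evaluable per group, 120 evaluable from 150 recruited (SAP 2.2).

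**Assumed, because the documents are silent.** The number per arm with no post-baseline assessment is varied from 0 to 10 of 50. Responders are set at 28 of 50 on active and 20 of 50 on placebo (56% v 40%; the 40% is the SAP's placebo example).

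**The plan's own figure.** n = [z(0.95)·√(2p̄(1−p̄)) + z(0.80)·√(p₁(1−p₁) + p₂(1−p₂))]² / (p₁−p₂)², with p̄ = (0.674 + 0.40)/2 = 0.537:

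- first term: 1.645 × √0.4973 = 1.160
- second term: 0.842 × √0.4597 = 0.571
- n = (1.731)² / 0.274² = 39.9, so 40 per group; power at 40 is 80.1%
- 120 / (1 − 0.20) = 150

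The sample size reproduces, and this point does not affect it.

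**Two patients traced through the rules.** Both are dosed and stop on Day 10.

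- Patient A attends an Early Termination Visit. A is in the full analysis set. SAP 3.5.2 and 3.5.3 allow that assessment to be assigned only to an adjacent planned visit (Day 1 or Day 28), so Day 84 is missing and SAP 3.5.1 scores a failure.
- Patient B attends no further visit. B is in neither the full analysis set nor the valid cases set, and is in no responder denominator. The valid cases set keeps patients who stop for an IMP-related adverse event, but that does not help B, because the set starts from the full analysis set.

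**Effect on the rates.** If k of n patients are excluded and none is a responder, the arm's rate moves from r/n to r/(n−k). P-values are from an unstratified chi-square test without continuity correction.

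| Excluded active / placebo | Active | Placebo | Difference (points) | p |
|---|---|---|---|---|
| 0 / 0 (all counted, missing = failure) | 28/50 = 56.0% | 20/50 = 40.0% | 16.0 | 0.109 |
| 2 / 2 | 28/48 = 58.3% | 20/48 = 41.7% | 16.7 | 0.102 |
| 5 / 5 | 28/45 = 62.2% | 20/45 = 44.4% | 17.8 | 0.091 |
| 5 / 2 | 28/45 = 62.2% | 20/48 = 41.7% | 20.6 | 0.047 |
| 5 / 0 | 28/45 = 62.2% | 20/50 = 40.0% | 22.2 | 0.031 |
| 10 / 0 | 28/40 = 70.0% | 20/50 = 40.0% | 30.0 | 0.005 |
| 0 / 5 | 28/50 = 56.0% | 20/45 = 44.4% | 11.6 | 0.261 |

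**No true difference.** Suppose 40% of all patients respond in both arms. Excluding 10% of active and none of placebo gives 0.40/0.90 = 44.4% v 40.0%, an apparent 4.4-point benefit. The chance of a false result in favour of active, at the two-sided 0.10 level, rises from 5% to about 11% (normal approximation). Excluding 10% of placebo instead gives the same shift against active.

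**The case against.** - **Few patients may be affected.** Protocol 5.3.5.2 demands every effort to obtain the final evaluations, and a termination, follow-up or unscheduled visit would bring the patient into the set. This stands as a limit on size. It reduces such losses but cannot rule them out, and Table 14.1.4 plans for them.
- **The term is undefined.** Read literally, the Day 1 post-dose PK samples (Protocol 5.5.1.5) are post-baseline assessments, which would admit the PK subgroup (about 30 patients) on the first day. This stands, and it is a further reason to remove the condition from the co-primary analyses.
- **The condition has a use.** It does for change-from-baseline analyses and for last-observation-carried-forward (LOCF) summaries. The co-primary responder shells (Tables 14.3.3 and 14.3.15) are also titled LOCF, contrary to SAP 3.5.1. This stands: the shells must be aligned or the failure rule may not be applied.
- **Exclusions are disclosed.** Tables 14.1.1 and 14.1.4 give counts by arm, so a reader could divide responders by the number in the safety set. That recovers a crude rate, if the responder counts follow SAP 3.5.1, but not the stratified CMH odds ratio and its interval.
- **The trial is exploratory.** SAP 3.4 treats all p-values as descriptive. This stands: the harm is a distorted estimate, not a failed confirmatory test.

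A reader might infer that the definition favours MP1032 because poorly tolerated arms lose more patients early. The documents do not support that. They report no early losses by arm and no reasons for early stopping, and their only comparative tolerability figures (Protocol 3.2, phase IIa, 100 mg twice daily) show treatment-emergent events in 60.87% on MP1032 and 65.22% on placebo. Nor is the allowance of 30 non-evaluable patients in 150 a rate of loss before Day 28. 'Evaluable' is undefined and may cover missed Day 84 visits, poor compliance or prohibited medication.

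**Conclusion.** The point holds as a defect of definition. Under the plan as written, the co-primary denominators depend on whether a dosed patient is seen again after baseline. The failure rule makes that condition unnecessary for these endpoints, and no planned analysis counts the excluded patients.

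The bias cannot be sized or signed from the documents. Balanced losses matter little (16.0 to 17.8 points at five per arm). Unbalanced losses of five in one arm move the illustrated difference to 22.2 or 11.6 points, depending on the arm. These figures rest on assumed loss and responder counts, on excluded patients being non-responders (which SAP 3.5.1 would make them), and on an unstratified test in place of CMH. They do not show that any particular share of the design difference comes from the set definition. The correction is worth making because it costs almost nothing, even though the trial is exploratory.

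**What to change.** Before unblinding:

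1. In SAP 3.3.1, for the PASI 75 and PGA improvement analyses, delete the post-baseline-assessment condition. Use all randomised patients, excluding only those documented as never having taken IMP. A patient given IMP who does not return counts as dosed. This wording is needed because, outside the PK subgroup, the first dose is taken at home, and diaries and kits are checked only at later visits (Protocol 5.4.6 and 5.5.1.6). For a patient who never comes back, a requirement of proven dosing could bring the same exclusion back.
2. Score missing Day 84 PASI or PGA in this set as failure under SAP 3.5.1.
3. Align Table 14.1.4, and bring the LOCF-titled responder shells 14.3.3, 14.3.9, 14.3.15 and 14.3.18 into line with the failure rule.
4. Record the change in SAP 1.3, which now reports no modifications. Protocol section 6 allows statistical changes before database lock to be documented in the SAP without a protocol amendment.
5. Change-from-baseline analyses can keep using patients with data. If the condition stays for them, define which assessment satisfies it.

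No new data are needed. The cost is minor table edits and slightly lower reported response rates.
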